**Table 3: Schedule of Assessments: Phase 2**

Visit/Cycle:	Scrn	Cycle 1					Cycle 2			Cycle 3  – Cycle 12		Cycle 13 and beyond 	EOT 	Follow-up	Follow-up HSCT	Survival Follow-up	
		D -28	D1 	D2	D8	D15	D22	D1 	D2	D15	D1						D15
Informed Consent	X																
Review Entry Criteria	X																
Demographics	X																
Medical and Surgical History	X																
Medication History 	X																
Complete Physical Exam	X												X				
Limited Physical Exam		X		X	X		X			X		X					
Height  and Weight	X	X			X		X			X		X	X				
ECOG PS	X	X			X		X			X		X	X	X	X		
Vital Signs 	X				X		X			X			X			X	
Serial Vital Sign 		X															
Single 12-lead ECG 		Please refer to Table 5															
Serial Triplicate 12-lead ECGs 																	
ECHO/MUGA for LVEF	X									X 			X				
Gene Mutation Analysis 	X																
UGT1A1 Gene Testing	X																
Laboratory Evaluations:																	
Hematology 	X	X		X	X	X	X		X	X	X	X	X			X 	
Serum Chemistry 	X	X		X	X	X	X		X	X	X	X	X			X	
Coagulation Studies 	X	X			X		X			X		X	X			X	
Pregnancy Test 	X	X					X			X		X	X				
Bone Marrow Biopsy and Aspirate 	X						X			X		X	X			X 	

Visit/Cycle:	Scrn	Cycle 1					Cycle 2			Cycle 3  – Cycle 12		Cycle 13 and beyond 	EOT 	Follow-up	Follow-up HSCT	Survival Follow-up
Study Day:	D -28	D1 	D2	D8	D15	D22	D1 	D2	D15	D1	D15	D1		28 Days post Discon	Every 28 Days	Every 28 Days
Peripheral blood for molecular and functional studies of plasma, blasts and neutrophils 	X						X			X		X	X		X 	
Evaluate Extent of Disease and Response to Treatment 							X			X		X	X 		X 	
Transfusion Assessment 	X						X			X		X	X 		X 	
Study Drug Administration 		X	X	X	X	X	X	X	X	X	X	X 				
Compliance Assessment 							X			X		X	X			
PK/PD Assessment 		Please refer to Table 5														
Adverse Events	X	X	X	X	X	X	X	X	X	X	X	X 	X	X 		
Concomitant Medications / Procedures	X	X	X	X	X	X	X	X	X	X	X	X 	X	X	X	
Study Completion 														X	X	X

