17. Bone marrow aspirates and core sampling should be performed and analyzed at the local site's laboratory in accordance with the International Council for Standardization in Hematology (ICSH) Guidelines ([Lee, et al. 2008](#)) (see [Section 10.7](#)). Investigator assessment of cytogenetic risk group at baseline and results of the bone marrow assessments performed for the evaluation of clinical activity will be collected for an independent review during Phase 2 of the study. Analyses should include cytogenetics and flow cytometry according to institutional standards and results should be recorded in the eCRFs. Studies should be conducted on peripheral blood samples if bone marrow aspirate is not available (e.g., a "dry" tap).
18. Evaluation of disease response, including bone marrow and peripheral blood for plasma and IDH2-mutated cells to be conducted on C2D1, every 28 days during treatment through at least Month 12 (see [Section 10.8.1](#)). Evaluation should be independent of dose delays and/or dose interruptions, and/or at any time when progression of disease is suspected. After at least 12 months, subjects in the Phase 2 portion of the trial, may have the extent of their disease assessed, including bone marrow biopsy, aspirates or peripheral blood based on their response to treatment.
19. Subjects will have the extent of their disease assessed based on modified IWG criteria or other appropriate response criteria for the malignancy under study (see [Section 10.8](#)).
20. Response to treatment is to be assessed at this visit if the subject discontinues treatment for reasons other than disease progression.
21. Subjects are also to be evaluated for RBC and platelet transfusions (dates and units administered) and associated hemoglobin levels and/or platelet counts at each response assessment and as clinically indicated.

- The daily dose on C1D1, C1D2, C2D1, C2D2 and C3D1 are to occur in clinic to accommodate PK/PD sampling (C1D1 and C2D1) or to allow for predose assessments (C1D2, C2D2 and C3D1).
- Treatment compliance is to be assessed based on return of unused drug as well as subject diaries.
- Refer to [Table 5](#) for complete serial PK/PD sampling schedule and to [Section 10.10](#) for details for blood sampling for 2-HG and  $\alpha$ -KG.

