All subjects are to be followed for survival status follow up every 3 months until death, withdrawal of consent, or end of study for survival.

56-Day transfusion independence rate: The rate of subjects who have been transfusion free for at least 56 consecutive days post baseline during treatment exposure period. Sensitivity analyses will be conducted for all duration of response/remission, time to response/remission, and EFS endpoints in which subjects who go on to receive bone marrow transplantation will be censored at the time of transplantation.

All time to event endpoints will be estimated using Kaplan-Meier methods. Point estimates and 95% confidence intervals will be provided where appropriate. Estimates of the median and other quantiles, as well as individual time points (e.g., 3-month, 6-month, and 12-month rates) will be produced. Additional details of the censoring rules will be specified in the Statistical Analysis Plan. Other measures of clinical activity will be evaluated including summaries of transfusion requirements and infection rates. Descriptive statistics will be used.

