9.1. Treatment Duration and Exposure

Duration of treatment (months) is defined as: $(\text{treatment end date} - \text{treatment start date} + 1) / 30.4$. The treatment start date is the date of the first dose of study drug, and the treatment end date is the last dose date. For subjects who are still on treatment at a data cut-off date, treatment end date will be the earlier date of data cut-off date and last day that the subjects take study drug.

Duration of treatment exposure (months) is defined as: $(\text{Treatment end date} - \text{treatment start date} + 28) / 30.4$. If death date is after treatment end date and earlier than 28 days after treatment end date, duration of treatment exposure is defined as: $(\text{Death date} - \text{treatment start date} + 1) / 30.4$.

Treatment duration and exposure will be summarized by investigator assessed best response for the combined Phase 1, Phase 2, and the combined Phase 1/2 R/R AML subjects and overall.

A subject data listing of study drug records will be provided.

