10.3.1.5. Overall Survival

Overall survival is defined as the time from first dose to the date of death due to any cause. Subjects alive will be censored at the last date known to be alive or a pre-specified data cut-off date, whichever is earlier. The last known alive date is the last non-imputed date of any subject record in the study database. This date may be the last visit date or last contact date that the subject is known to be alive. Subjects who only have a baseline record will be censored at the first dose date.

The OS will be primarily analyzed in the FAS for the Part 1 Expansion, the combined Phase 1, Phase 2, and the combined Phase 1/2 as described in items 2 to 5 of [Section 5.1](#). Due to the limited sample size of each total daily dose group, OS will not be analyzed for Phase 1 dose escalation.

The survival distribution of OS will be estimated using the KM methods. The 25th percentile, median and 75th percentile time with two-sided 95% CI will be provided. KM curves will be provided as well. In addition, KM methods will also be used to estimate the survival probabilities at 3, 6, 9 and 12 months.

Sensitivity analyses for OS will be conducted for the combined Phase 1, Phase 2 and the combined Phase 1/2 where transplanted subjects will be censored at HSCT.

10.3.1.6. 56-Day Transfusion Independence Rate

Subjects who achieved post-baseline 56-day RBC transfusion independence i.e. without RBC transfusion for at least 56 consecutive days post baseline during treatment exposure period will be summarized by baseline RBC transfusion dependence status (Yes vs. No). Subjects with at least one transfusion during the baseline period are considered transfusion dependent at baseline. Baseline period is defined as 28 days before and 28 days after the first dose of treatment for Phase 1, and 56 days before the first dose date for Phase 2.

The post-baseline 56-day Platelet transfusion independence will be analyzed similarly. Subjects who achieved both RBC and Platelet 56-day transfusion independence post baseline during treatment exposure period will be summarized by the status of baseline transfusion dependence i.e. receiving at least one RBC and/or Platelet transfusion during baseline period. Transfusion data will be summarized for the combined Phase 1, Phase 2, and the combined Phase 1/2.

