15.4. Schedules of Assessments

Table 9 and Table 10 provide the schedules of assessments for subjects enrolled in Phase 1 and for subjects enrolled in the Phase 2 portion of the trial, respectively. Table 11 and Table 12 provide the PK and PD sampling and ECG schedule for subjects enrolled in Phase 1 and for subjects enrolled in Phase 2, respectively.

Table 9: Schedule of Assessments: Phase 1 (Dose Escalation and Part 1 Expansion)

Visit/Cycle:	Scrn	Day -3 ¹	Cycle 1				Cycle 2		Cycle 3 ⁴ – Cycle 12		Cycle 13 ³¹ and beyond	EOT ³	Safety Follow-up Visit	Follow-up HSCT ¹¹	Survival Follow- up
Study Day:	D -28		D1 ²	D8	D15 ²	D22	D1 ²	D15	D1 ²	D15	D1		28 days post Discon.	Every 28 Days	Every 28 Days
Informed Consent	X														
Review Entry Criteria	X														
Demographics	X														
Medical and Surgical History	X														
Medication History	X														
Complete Physical Exam	X										X				
Limited Physical Exam		X	X	X	X		X		X		X				
Height ⁶ and Weight	X	X	X		X		X		X		X	X			
ECOG PS	X	X	X		X		X		X		X	X	X		
Vital Signs ⁷	X				X		X		X			X			
Serial Vital Signs ^{7,8}		X	X												
Single 12-lead ECG ⁹		Please refer to Table 11													
Serial single 12-lead ECG ⁹		Please refer to Table 11													
ECHO/MUGA for LVEF	X								X ¹⁰			X ¹⁰			
Gene Mutation Analysis ¹¹	X														
UGT1A1 Gene Testing	X														

Visit/Cycle:	ScrN	Day -3 ^{1,2}	Cycle 1				Cycle 2		Cycle 3 ⁴ – Cycle 12		Cycle 13 ³¹ and beyond	EOT ³	Safety Follow-up Visit	Follow-up HSCT	Survival Follow-up
			Study Day: D -28	D1 ²	D8	D15 ²	D22	D1 ²	D15	D1 ²	D15		D1	28 days post Discon.	Every 28 Days
Laboratory Evaluations:															
Hematology ¹²	X	X	X	X	X	X	X	X	X	X	X	X		X ¹³	
Serum Chemistry ¹⁴	X	X	X	X	X	X	X	X	X	X	X	X			
Coagulation Studies ¹⁵	X	X	X		X		X		X		X	X			
Fasting Lipid Panel ¹⁶	X								X ¹⁶		X	X			
Pregnancy Test ¹⁷	X	X	X				X		X		X	X			
Bone Marrow Biopsy and Aspirate ^{18,19}	X				X		X		X		X	X		X ¹³	
Peripheral blood for IDH2-mutated cells/leukemic blasts, plasma, and neutrophils ¹⁹	X				X		X		X		X	X		X ¹³	
Evaluate Extent of Disease and Response to Treatment ^{19,20}					X		X		X		X	X ²¹	X	X ¹³	
Transfusion Assessment ²²	X				X		X		X		X	X ²¹	X	X ¹³	
Single-dose Study Drug Administration ^{23,24}		X													
Study Drug Administration ²⁴			X	X	X	X	X	X	X	X	X ³²				
Compliance Assessment ²⁵							X		X		X	X			
PK/PD Assessments ²⁶		Please refer to Table 11													
Blood Sampling ²⁶															
Urine Sampling ²⁶															

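### The 56-day transfusion-independence search has no stated end; on the SAP's own exposure formula up to 27 of the 56 days can fall after the last dose, including after HSCT or new therapy

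*SAP*

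**What the plan says.** Transfusion independence over 56 days is a key secondary endpoint (SAP 4.2.1 and 10.3). For red cells, SAP 10.3.1.6 looks for subjects "without RBC transfusion for at least 56 consecutive days post baseline during treatment exposure period"; platelets are handled in the same way. Protocol 12.5.7 refers to the same period: "The rate of subjects who have been transfusion free for at least 56 consecutive days post baseline during treatment exposure period". Neither text gives the last day of the period. Neither says what happens at transplant, at new anti-cancer therapy, or on days for which transfusion data were not collected.

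SAP 9.1 is the only section that gives treatment exposure a length. It defines two measures. Duration of treatment is end minus start plus 1 day. The other opens "Duration of treatment exposure (months) is defined as" and continues as treatment end minus treatment start plus 28 days, over 30.4. It has one shortening rule, "If death date is after treatment end date and earlier than 28 days after treatment end date", in which case exposure ends at death.

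Under SAP 10.3.1.6, the Phase 1 baseline period is 28 days on either side of the first dose, and the Phase 2 baseline period is the 56 days before it.

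In the Phase 2 schedule (Protocol Table 3), the row "Transfusion Assessment 21" is marked at screening, Day 1 of Cycle 2 and of later cycles, end of treatment (EOT) and HSCT follow-up. It is blank at the 28-day Follow-up. In the Phase 1 schedule (SAP Table 9), the row "Transfusion Assessment ²²" is marked at the 28-day safety follow-up.

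**The concern.** The endpoint is meant to describe freedom from transfusion while AG-221 is acting. If the period follows SAP 9.1, nearly half of the qualifying run can fall after the drug has stopped. Those days can include time after HSCT or under another anti-leukemic treatment, so a run could be credited to AG-221 that it did not produce.

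The endpoint asks only whether one 56-day run exists. Lengthening the search can therefore turn non-qualifiers into qualifiers and never the reverse. The two phases also enter the combined Phase 1/2 summary with different minimum times on drug and different marked assessments after the last dose.

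**Working it through.** The plan states no expected rate, precision or sample size for this endpoint, so there is no figure to reproduce. The check is day arithmetic on SAP 9.1 and 10.3.1.6, followed by a comparison with the other endpoints.

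**1. Where the window ends.** Let *d* be the number of days from first to last dose inclusive, so end − start = *d* − 1.
- Exposure days = (*d* − 1) + 28 = *d* + 27.
- Counting from the first dose, the last exposure day is last dose + 27.

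**2. Phase 2 minimum.** Baseline lies before the first dose, so post-baseline time is taken to start on the first dosing day.
- Requirement: *d* + 27 ≥ 56, so *d* ≥ 29.
- *d* = 28 gives 55 days and fails; *d* = 29 gives 56 and qualifies.
- Off-drug share at the minimum: 27/56 = 48.2%.
- With the search ended at the last dose: *d* ≥ 56.

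Subjects with 29 to 55 days on drug can therefore qualify only because of the tail. Longer-treated subjects are affected only if their sole run needs days after the last dose.

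**3. Phase 1 minimum.** Suppose baseline runs through study Day 28.
- Requirement: *d* + 27 − 28 ≥ 56, so *d* ≥ 57.
- With the search ended at the last dose: *d* − 28 ≥ 56, so *d* ≥ 84.
- If baseline is counted through Day 29, these become 58 and 85.

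Up to 27 off-drug days can count in Phase 1 too, but only after a much longer time on drug.

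**4. How the same events are handled elsewhere.**

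| Endpoint | Subsequent anti-cancer therapy | HSCT |
|---|---|---|
| DOR (SAP 10.3.1.4, Table 3) | Censored | Sensitivity analysis censored at last adequate assessment before HSCT |
| EFS (SAP 10.3.2.1) | Censored under Table 3 | Sensitivity analysis in Protocol 12.5.7 |
| OS (SAP 10.3.1.5) | No rule | Sensitivity analysis censored at HSCT |
| Transfusion independence | No rule | No rule |

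The Protocol 12.5.7 transplant-censoring analyses cover duration, time-to-response and EFS endpoints, not this one. The general exclusion in SAP 5.1 applies only to data after AG-221 is restarted following HSCT.

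**5. Assessments in the Phase 2 tail.** EOT falls 0 to 5 days after the last dose. For a subject not in HSCT follow-up, 27 − 5 = 22 to 27 − 0 = 27 off-drug days come after the last marked transfusion assessment. The concomitant medications and procedures row is marked at the 28-day Follow-up, so these days are not necessarily unobserved.

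**6. Size.** The number of subjects affected is not in the documents. With 125 subjects in the denominator, each reclassified subject moves the rate by 1/125 = 0.8 percentage points. The step is larger within the baseline-dependence groups used in SAP 10.3.1.6, whose sizes are not given.

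**The case against.** **The window is inferred.** SAP 10.3.1.6 does not cite 9.1, and 9.1 defines a duration for exposure summaries. This is correct. But if 9.1 does not apply, a key secondary endpoint has no end date at all, and the same paragraph still has to be written.

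**A 28-day tail matches the safety windows.** SAP 11.1 and 11.3 use 28 days after last dose for treatment-emergent events and on-treatment deaths. There the tail is cautious because it adds adverse outcomes. Here it adds favourable ones, so the parallel does not justify it.

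**The endpoint is descriptive.** It has no success threshold, and SAP 10.1 treats multiplicity as not of concern. That limits the consequence but not the bias in the reported rate.

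**The stronger reading, that unassessed time is scored as transfusion-free, is not established.** A reader might infer it from the blank Phase 2 cell, but the documents do not support it:
- Transfusions are recorded with dates and units, and SAP 15.2 has imputation rules for transfusion dates.
- Concomitant procedures are collected at the 28-day Follow-up, and the HSCT follow-up column carries a transfusion mark (if performed).
- A blank cell is weak evidence: in the same table the LVEF row is blank at Follow-up, yet footnote 10 requires it there.
- Text on concomitant medications and procedures is partly redacted, so a missing source rule cannot be held against the plan.

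**Two long assessment gaps are also tempting and should not be used.**
- For a progression stop on cycle Day 28, one might count 27 + 28 = 55 days since the last assessment. That reads EOT footnote 20, "Response to treatment is to be assessed at this visit if the subject discontinues treatment for reasons other than disease progression", as cancelling the transfusion assessment, but it conditions only the response assessment. Disease is also assessed whenever progression is suspected, and transfusions are evaluated at each response assessment, so a progression stop normally has its own.
- From Cycle 13 one might count 3 × 28 = 84 days. Footnote 31 keeps concomitant medication capture at every 28 days, on the row that also covers procedures.

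**Conclusion.** The point holds in this form: the search period has no stated end, and on the SAP's only exposure definition it reaches 27 days past the last dose, cut only at death. Up to 27 of the 56 qualifying days can be off drug in either phase. The minimum time on drug is 29 days in Phase 2 and about 57 in Phase 1, against 56 and about 84 if the search ended at the last dose. HSCT and new anti-cancer therapy do not stop the run. Relative to ending at the last dose, the effect on the rate is zero or favourable; its size cannot be derived from the documents.

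This rests on reading the period through SAP 9.1, and on Phase 2 post-baseline time starting with the first dosing day. If that day belongs to baseline, the Phase 2 minimum is 30.

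The unmarked Phase 2 28-day Follow-up, against a marked one in Phase 1, is a lesser matter. It creates a risk of under-ascertainment that the documents neither show nor exclude.

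**What to change.** In SAP 10.3.1.6, state that the search for a 56-day run ends at the earliest of:
- the last AG-221 dose;
- the start of HSCT conditioning;
- the start of subsequent anti-cancer therapy;
- death;
- the last date through which transfusion records, from the transfusion or concomitant-procedure pages, are complete.

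Apply the rule to both phases and to red cells, platelets and the two combined. Once the last dose caps the search, the HSCT and new-therapy dates should seldom bind, but stating them leaves no case open. Keep the SAP 9.1 window (end minus start plus 28 days) as a sensitivity analysis, so that the effect of the tail can be seen. Because Protocol 12.5.7 uses the same undefined period, list the change in SAP 13.

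The cost is one paragraph, an entry in SAP 13 and minor reprogramming. Last-dose, transplant, new-therapy and death dates are already collected; a start date for conditioning should be confirmed in the database. The reported rate may be slightly lower.

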10.3.2. Other Secondary Endpoints

The other secondary endpoints include rate of EFS, DOCR, DOCR/CRh, TTR, TTBR, TTCR, and TTCR/CRh.

10.3.2.1. Event-Free Survival

Event-free survival is defined as the interval from the date of the first dose to the date of documented relapse, progression, or death due to any cause, whichever occurs first. Subjects without an EFS event will be censored according to the rules in [Table 3](#). Subjects who only have a baseline record will be censored at date of the first dose.

The analysis methods for EFS are similar to those for DOR. The KM method will be used to estimate the EFS probabilities at 3, 6, 9 and 12 months. The EFS based on IRAC assessment will also be analyzed for Phase 2 R/R AML subjects.

EFS will be analyzed in the FAS for Part 1 Expansion, the combined Phase 1, Phase 2, and the combined Phase 1/2. Due to the limited sample size of each total daily dose group, EFS will not be analyzed for Phase 1 dose escalation.

10.3.2.2. Duration of Complete Response

Among subjects who achieve a CR, DOCR is defined as the time from the date of the first documented CR to the earlier date of documented disease relapse or death due to any cause, using similar censoring as in [Table 3](#).

Kaplan-Meier methods will be used to estimate DOCR in the FAS subjects with CR for Part 1 Expansion, the combined Phase 1, Phase 2, and the combined Phase 1/2. The corresponding KM curves will be provided as well. The DOCR assessed by IRAC will be analyzed to provide supportive evidence.

10.3.2.3. Duration of CR/CRh

Among subjects who achieve a CR/CRh, DOCR/CRh is defined as the time from the date of the first documented CR or CRh to the earlier date of documented disease relapse or death due to any cause, using similar censoring as in [Table 3](#).

Kaplan-Meier methods will be used to estimate DOCR/CRh in the FAS subjects with CR/CRh for the combined Phase 1, Phase 2, and the combined Phase 1/2. The corresponding KM curves will be provided as well. The DOCR/CRh analyses will be based on IRAC assessments.

10.3.2.4. Time to Response

Time to response will be assessed from the date of first dose to the date of first occurrence of response of CR, CRi, CRp, PR, or mCR/MLFS.

Time to response will be summarized using descriptive statistics in subjects who respond in the FAS for Phase 1 dose escalation, Part 1 Expansion, the combined Phase 1, Phase 2, and the combined Phase 1/2. Time to response will also be summarized by cycle. The time to response by IRAC will also be analyzed.

10.3.2.5. Time to Best Response

Time to best response will be assessed from the date of first dose to the date of first occurrence of best response.

Time to best response will be summarized using descriptive statistics in subjects who respond in FAS for Phase 1 dose escalation, Part 1 Expansion, the combined Phase 1, Phase 2, and the combined Phase 1/2. Time to best response will also be summarized by cycle. The time to best response by IRAC will be analyzed.

10.3.2.6. Time to Complete Response

Time to CR will be summarized using descriptive statistics as assessed from the date of first dose to the date of first response (CR) in subjects with documented CR in FAS for Phase 1 dose escalation, Part 1 Expansion, and the combined Phase 1, Phase 2, and the combined Phase 1/2. Time to CR will also be summarized by cycle. The time to complete response by IRAC will be analyzed.

